3.13 Treatment Administration Assessment Form

The treatment administration assessment form, as part of the electronic case report form (eCRF), will be completed by the investigator on Day 1 after study drug administration per Section 2.1.

The investigator will evaluate whether the updated (test) or the currently-approved (comparator) DEX PS DDS Applicator dispensed the DEX PS DDS Implant in the vitreous cavity and performed as intended. The position of the DEX PS DDS Implant in the vitreous cavity will be defined¹ as follows:

- Position 1 (P1) = presence of the DEX PS DDS Implant in contact with pars plana and/or ciliary processes.
- Position 2 (P2) = presence of the DEX PS DDS Implant anterior to the equator but with no part of it in contact with pars plana and/or ciliary processes. Equator is identified based on the location of the vortex veins.
- Position 3 (P3) = presence of the DEX PS DDS Implant posterior to the equator. Equator is identified based on the location of the vortex veins.

If the DEX PS DDS Implant is visible between P2 and P3 positions, then it should be marked as P2.

COVID-19 Pandemic-Related Acceptable Protocol Modifications

There are no pandemic or natural disaster-related protocol modifications for the treatment administration assessment form, other than those specified in Section 2.

3.14 Subject Withdrawal from Study

All attempts must be made to determine the primary reason for discontinuation of study drug or study participation. The information will be recorded on the appropriate eCRF page. However, these procedures should not interfere with the initiation of any new treatments or therapeutic modalities that the investigator feels are necessary to treat the subject's condition. Following discontinuation of study drug, the subject will be treated in accordance with the investigator's best clinical judgment, irrespective of whether the subject decides to continue participation in the study.

3.15 Unscheduled Visits

An Unscheduled Visit should be performed when the subject comes in for a medical visit for evaluation and assessment. During Unscheduled Visits, blood and urine samples may be obtained for tests, at the investigator's discretion. Visits to only retest a lab will not be considered an Unscheduled Visit.

4 SAFETY MANUAL

4.1 Methods and Timing of Safety Assessment

All serious and nonserious adverse events (AEs) that could be related to study procedures will be collected from the time the subject signed the study specific informed consent until study drug administration. From the time of study drug administration until 30 days after the last dose of study drug or study treatment, all nonserious and serious AEs will be collected whether solicited or spontaneously reported by the subject. After 30 days following the last dose of study drug or completion of study treatment only spontaneously reported serious adverse events (SAEs) will be collected (nonserious AEs will not be collected).

4.2 Reporting Adverse Events, Product Complaints, and Intercurrent Illnesses

In the event of an SAE, whether associated with study drug or not, the investigator will notify Clinical Pharmacovigilance within 24 hours of the site being made aware of the SAE by entering the SAE data into the electronic data capture (EDC) system. Serious adverse events that occur prior to the site having access to the RAVE® system, or if RAVE is not operable, should be documented on the SAE non-CRF forms and emailed (preferred route) or faxed to Clinical Pharmacovigilance within 24 hours of the site being made aware of the SAE.

Email: [contact]
FAX to: [contact] Backup: [contact]

For safety concerns, contact the Ophthalmology Safety Team at:

Ophthalmology Safety Team
[name]
[name]
Toll Free: [contact]
Email: [contact]

For any subject safety concerns, please contact the physician listed below:

Primary Therapeutic Area Medical Director

EMERGENCY MEDICAL CONTACT:

[REDACTED] MD

AbbVie Inc.

[name]
[name]

Contact Information:

Mobile: [REDACTED]

Email: [REDACTED]

In emergency situations involving study subjects when the primary Therapeutic Area Medical Director is not available by phone, please contact the 24-hour AbbVie Medical Escalation Hotline where your call will be re-directed to a designated backup AbbVie Therapeutic Area Medical Director:

[REDACTED]
[contact]

The sponsor will be responsible for Suspected Unexpected Serious Adverse Reactions (SUSAR) reporting.

In the event of a product complaint occurring, the following procedure needs to be followed:

- Take pictures of the product immediately after the complaint occurs, focusing on the area with a complaint or defect if possible
- Do not discard the product
- Quarantine the product in question in appropriate container (such as a SHARPS container)
- Complete the Product Complaint eCRF within 24 hours of the event
- Hold sample at the site location until disposition or further instructions are provided by Sponsor's Product Complaint Team for possible product return.

For any questions, the site may email the Sponsor's Product Complaint Team at
[contact].

COVID-19 Pandemic-Related Acceptable Protocol Modifications

Supplemental study case report forms should be completed in the event of COVID-19-related missed visits, study drug interruptions or discontinuations, or AEs (including capture of specific signs/symptoms of infection and testing results).

Severe acute respiratory syndrome coronavirus 2 infections should be captured as AEs. If the event meets the criteria for a SAE, then follow the SAE reporting directions per the protocol and above. The following COVID-19-related supplemental eCRFs should be completed (for both serious and nonserious events):

- COVID-19 Supplemental Signs/Symptoms
- COVID-19 Status Form

Reactions known to be associated with the SARS-CoV-2 vaccine should be reported as AEs. If the event meets the criteria for an SAE, then follow the SAE reporting directions. All AEs associated with the SARS-CoV-2 vaccine will be linked to the vaccine on the COVID-19 Vaccine eCRF.

5 COUNTRY-SPECIFIC REQUIREMENTS

5.1 SUSAR Reporting

AbbVie will be responsible for SUSAR reporting for the study drug in accordance with global and local guidelines and the Appendix of the Investigator Brochure will serve as the reference safety information (RSI). The RSI in effect at the start of a Development Safety Update Report reporting period serves as the RSI during the reporting period. For follow-up reports, the RSI in place at the time of occurrence of the 'suspected' Serious Adverse Reaction will be used to assess expectedness.

6 STUDY DRUG

6.1 Treatments Administered

The study drug (DEX PS DDS Implant 0.7 mg) will be administered into the SE on Day 1 (Section 2.1).

Study drug must not be dispensed without contacting the interactive response technology (IRT) system. Study drug may only be dispensed to subjects enrolled in the study through the IRT system.

6.2 Packaging and Labeling

The DEX PS DDS Implant 0.7 mg will be preloaded in the updated DEX PS DDS Applicator that incorporates the final, to-be-marketed design (test) or the currently-approved DEX PS DDS Applicator (comparator).

Both the updated and currently-approved DEX PS DDS Applicators will be provided in a sealed pouch and the pouch will be contained within a carton.

Both the pouch and the carton will be labeled as required per country requirement. The labels must remain affixed to the pouch and carton. All blank spaces should be completed by site staff prior to dispensing to subject.

Storage and Disposition of Study Drug

Study drug must be stored at 15° to 30°C (59° to 86°F).

The study drug is for investigational use only and is to be used only within the context of this study. The study drug supplied for this study must be maintained under adequate security and stored under the conditions specified on the label until dispensed for subject use or destroyed on site as appropriate.

Sites are responsible for maintaining the study drug according to the storage conditions specified on the clinical label and monitoring for temperature excursions with the use of a calibrated continuous temperature monitoring device (for example, chart recorders and/or acceptable calibrated min/max thermometers) or continuous monitoring systems. Specific guidance on appropriate temperature monitoring and temperature excursions reporting requirements will be provided separately.

6.3 Method of Assigning Subjects to Treatment Groups

This is a Phase 3b, prospective, randomized, open-label, two- arm, 7-day clinical study in subjects with macular edema due to retinal vein occlusion (RVO) (branch retinal vein occlusion [BRVO] or central retinal vein occlusion [CRVO]) or diabetic macular edema (DME) to support the evaluation of the updated DEX PS DDS Applicator (that incorporates the final, to be marketed design) and demonstrate that it delivers the DEX PS DDS Implant to the vitreous cavity and is suitable for commercial use in patients with macular edema due to retinal disease. Eligible subjects will be administered DEX PS DDS Implant 0.7 mg in the SE on Day 1. Approximately 54 subjects will be enrolled in this study and randomly assigned in a 2:1 ratio to receive the DEX PS DDS implant using either the updated applicator (test) or the currently-approved applicator (comparator), respectively.

At the Screening/Baseline visit, all subjects will be assigned a unique subject number using the IRT. For subjects who do not meet the study selection criteria, the site personnel must contact the IRT system and identify the subject as a screen failure.

Subjects who are enrolled will retain their subject number assigned at the Screening/Baseline visit throughout the study. Upon receipt of study drug, the site will acknowledge receipt in the IRT system.

Contact information and user guidelines for IRT use will be provided to each site.

6.4 Selection and Timing of Dose for Each Subject

Eligible subjects will be administered DEX PS DDS Implant 0.7 mg in the SE on Day 1, in an open-label manner. Approximately 54 subjects will be enrolled in this study and randomly assigned in a 2:1 ratio to receive the DEX-PS-DDS implant using either the updated applicator (test) or the currently-approved

applicator (comparator), respectively. The study drug will be administered by the investigator after all other Day 1 procedures are completed (except for the treatment administration assessment form [completed by the investigator] and ophthalmoscopy [indirect], which will be performed following study drug administration).

7 APPENDICES

7.1 Biomicroscopy Exam (slit lamp)

Biomicroscopic examinations will be performed using a slit lamp. The examinations will include determination of ophthalmic medical observations/complications, evaluation of the condition of the eyelids, conjunctiva, cornea, anterior chamber, iris/pupil, and lens.

Eyelid/Eyelid Margins/Lashes:

Edema

0 (None) = No edema
+0.5 (Trace) = Localized, minimal (trace) swelling
+1 (Mild) = Localized, mild swelling
+2 (Moderate) = Diffuse, moderate swelling
+3 (Severe) = Diffuse, severe swelling

Erythema

0 (None) = No erythema
+0.5 (Trace) = Localized, minimal (trace), flush reddish color
+1 (Mild) = Localized, mild, flush reddish color
+2 (Moderate) = Diffuse reddish color encompassing the entire lid margin
+3 (Severe) = Deep diffuse reddish color of lid margins and superior and/or inferior eyelid

Conjunctiva (Bulbar):

Hyperemia

0 (None) = No hyperemia
+0.5 (Trace) = Minimal (trace) flush, reddish color
+1 (Mild) = Mild flush, reddish color
+2 (Moderate) = Bright red color
+3 (Severe) = Deep, bright, diffuse redness

Edema

0 (None) = No edema
+0.5 (Trace) = Localized, minimal (trace) swelling
+1 (Mild) = Localized, mild swelling
+2 (Moderate) = Diffuse, moderate swelling
+3 (Severe) = Diffuse, severe swelling

Conjunctiva (Palpebral):Hyperemia

0 (None) = No hyperemia
+0.5 (Trace) = Minimal (trace) flush, reddish color
+1 (Mild) = Mild flush, reddish color
+2 (Moderate) = Bright red color
+3 (Severe) = Deep, bright, diffuse redness

Edema

0 (None) = No edema
+0.5 (Trace) = Localized, minimal (trace) swelling
+1 (Mild) = Localized, mild swelling
+2 (Moderate) = Diffuse, moderate swelling
+3 (Severe) = Diffuse, severe swelling

Cornea:Edema

0 (None) = No edema
+0.5 (Trace) = Localized, minimal (trace) epithelial haze
+1 (Mild) = Dull glass appearance of epithelium that may include fine localized microcystic changes
+2 (Moderate) = Dull glass appearance of the epithelium with large number of cystic changes with or without stromal edema
+3 (Severe) = Epithelial bullae and/or stromal edema, localized or diffuse, with or without stromal striae

Punctate Epithelial Staining (includes superficial punctate keratopathy, punctate epithelial erosion, and punctate epithelial keratopathy)

0 = No staining
+0.5 = Trace
+1 = Mild
+2 = Moderate
+3 = Severe

Anterior Chamber:

For the measurements of cells and flare based on Standardized Uveitis Nomenclature (SUN) criteria², the following settings should be used:

- 1 x 1 mm slit beam
- High magnification
- Highest slit lamp voltage
- Low ambient lighting

- Illumination angle of 45°
- Same grader and slit lamp whenever possible

The Anterior Chamber will be evaluated, at a minimum, for presence of the following pathologies:

- Cells
 - 0 = 0 cells
 - +0.5 = 1-5 cells (trace)
 - +1 = 6-15 cells
 - +2 = 16-25 cells
 - +3 = 26-50 cells
 - +4 = > 50 cells
- Flare
 - 0 = None: No flare seen
 - +1 = Faint: Faint flare seen
 - +2 = Moderate: Iris and lens details clear
 - +3 = Marked: Iris and lens details hazy
 - +4 = Intense: Fibrin or plastic aqueous
- Anterior Synechiae
- Hypopyon – if hypopyon is present provide details and if applicable levels in millimeters (mm)

Iris/Pupil:

The iris/pupil will be evaluated for pathology. If pathology is present, it will be described.

Rubeosis Iridis

- 0 = No visible rubeosis iridis
- +0.5 = Trace visible rubeosis iridis
- +1 = Obvious vessels in 1 quadrant (≤ 90 degrees)
- +2 = Obvious vessels 2-3 quadrants (91-270 degrees)
- +3 = Obvious vessels 4 quadrants (271-360 degrees)

7.2 Lens Assessment

Lens Status:

Lens status will be assessed as phakic, pseudophakic, or aphakic. The lens (including the posterior capsule when visible, e.g., post-lens extraction) will also be evaluated for pathology. If pathology is present, it will be described.

Cataract Assessment (Phakic eyes only):

Under dilated examination, the presence and severity of nuclear, cortical, and posterior subcapsular cataract lens opacities will be evaluated according to the Age-Related Eye Disease Study Clinical Lens Grading Protocol. Biomicroscopic findings will be compared with standard photographs. AbbVie will supply the site with a copy of the standard photographs.³

Pupils should be dilated to at least 5 mm. The slit lamp should be used at 10x magnification. Grading will be performed as described below.

- Nuclear Sclerosis
 - Adjust the slit beam to a width of 0.3 mm and a height of 8.0 mm.
 - Orient the slit beam at 45° to the viewing axis.
 - Compare the slit lamp appearance with Nuclear Standard Photograph #2. The primary considerations are: the opalescence (reflectance) of the nucleus and the blurring of the normal landmarks, i.e., the dark interval at the center of the nucleus (the "sulcus") and the short, bright bands adjacent to it anteriorly and posteriorly (the "lentils," so named for their somewhat bean-like shape).
 - Standard Photographs. Only Nuclear Standard Photograph #2 is used in grading. Standard Photographs #1 and #3 are provided as examples of lenses that have less and more nuclear sclerosis than Standard Photograph #2.
 - Grading scale
 - I. Opacity is absent
 - II. Opacity is present, but less than Standard Photograph #2
 - III. Opacity is present and as severe as or worse than Standard Photograph #2
- Posterior Subcapsular (PSC) Opacities
 - Use retroillumination and include PSC opacities visible with it.
 - Standard Photographs. Only PSC Standard Photograph #2 is used for grading. PSC Standard Photograph #2 with lines at the borders of the opacity is provided for reference.
 - Grading scale
 - IV. Opacity is absent
 - V. Opacity is present, but less than Standard Photograph #2
 - VI. Opacity is present and as severe as or worse than Standard Photograph #2
- Cortical Opacities
 - Use retroillumination.
 - Include both anterior and posterior cortical opacities that are visible with retroillumination.
 - Combine all opacities and compare total area with Cortical Standard Photograph #2 (about 25% of the visible lens).

- Standard photographs. Only Cortical Standard Photograph #2 is used in grading. Standard #2 with lines at the borders of the opacities is provided for reference.
- Grading scale
 - VII. Opacity is absent
 - VIII. Opacity is present, but less than Standard Photograph #2
 - IX. Opacity is present and as severe as or worse than Standard Photograph #2

Posterior Capsule Assessment (aphakic or pseudophakic eyes only)

When visible, an assessment of the posterior capsule will be performed to determine the location of capsular opacification, if any, and whether the capsular bag is intact.

7.3 Ophthalmoscopy (indirect)

Dilated Fundoscopic Examination

The fundus assessments should be conducted through a dilated pupil. The examinations will include evaluation of the lens, vitreous, optic nerve, macula, and retina. The investigator should note if the pupil dilated normally.

Vitreous:

(1 x 3 mm beam in anterior vitreous).⁴

Cells

0 = None
+0.5 = 1-10 cells
+1 = 11-20 cells
+2 = 21-30 cells
+3 = 31-100 cells
+4 = > 100 cells

Note if the condition is not evaluable.

Vitreous Haze

Vitreous haze will be graded by viewing the optic disc and posterior retina using the following settings and by comparing the haze against a photographic standardized scale⁵ according to the chart provided by AbbVie.

- Indirect ophthalmoscope and a 20-diopter lens
- Illumination set to mid-power
- Large beam
- Low ambient lighting
- Same grader and indirect ophthalmoscope whenever possible

The scale is categorized as follows:

0 = No inflammation

+0.5 = Trace inflammation (slight blurring of the optic disc margins and/or loss of the nerve fiber layer reflex)

+1 = Mild blurring of retinal vessels and optic nerve

+2 = Moderate blurring of optic nerve head

+3 = Marked blurring of optic nerve head

+4 = Optic nerve head not visible

Note if the condition is not evaluable.

Vitreous Hemorrhage

Vitreous hemorrhage will be evaluated for severity. Indicate whether or not it is localized to the injection site.

0 = No visible evidence of hemorrhage on fundus ophthalmoscopic exam

+0.5 = Retinal detail is visible; trace hemorrhage is present

+1 = Retinal detail is visible; mild hemorrhage is present

+2 = Large retinal vessels are visible; central retinal detail is not visible

+3 = Red reflex is visible; no central retinal detail is seen posterior to the equator

+4 = No red reflex

Posterior Vitreous Detachment

The presence or absence of a posterior vitreous detachment will be evaluated. Note if the condition is not evaluable.

Optic Nerve:

The optic nerve will be evaluated for pathology. If pathology is present, it will be described. It will be noted if the condition is not evaluable.

Cup/Disc ratio will be reported using a 0.0 to 1.0 scale. It will be noted if the condition is not evaluable.

Macula:

The macula will be evaluated, at a minimum, for the presence or absence of the following pathologies. Note if the condition is not evaluable.

- Intraretinal fluid
- Subretinal fluid
- Intraretinal hemorrhage
- Subretinal hemorrhage
- Rhegmatogenous detachment
- Tractional detachment
- Pigment epithelial detachment

Retina Periphery:

The retina periphery will be evaluated, at a minimum, for presence or absence of the following pathologies. Note if the condition is not evaluable.

- Retinal hemorrhage
- Retinal tear (specify location in clock hours)
- Rhegmatogenous retinal detachment with or without macular detachment
- Tractional retinal detachment with or without macular detachment
- Exudative retinal detachment with or without macular detachment
- Round (atrophic) retinal hole
- Lattice degeneration

1.0 Introduction

This Statistical Analysis Plan (SAP) describes the statistical analyses for updated DEX PS DDS applicator study 1491-801-007, evaluation of an updated dexamethasone posterior segment drug delivery system applicator in participants with macular edema due to retinal diseases.

The SAP will not be updated in case of administrative changes or amendments to the protocol unless the changes impact the analysis.

Unless noted otherwise, all analyses will be performed using SAS Version 9.4 (SAS Institute Inc., Cary, NC 27513) or later under either or both the Linux and UNIX operating systems.

This SAP includes changes to analyses described in the protocol. Details are outlined in Section [14.0](#).

2.0 Study Design and Objectives

2.1 Objectives, Hypotheses and Estimands

[figure not shown]
The primary objective is to demonstrate that the updated DEX PS DDS applicator (that incorporates the final, to-be-marketed design) delivers the DEX PS DDS Implant to the vitreous cavity and is suitable for commercial use in subjects with macular edema due to retinal diseases.

There is no defined clinical [hypothesis](#) or estimands for this study.

2.2 Study Design Overview

The schematic of the study is shown in [Figure 1](#).

Figure 1. Study Schematic

DEX PS DDS = Dexamethasone Posterior Segment Drug Delivery System

2.3 Treatment Assignment and Blinding

All subjects will be treated with DEX PS DDS Implant in an unmasked, open-label manner. Subjects will be randomly assigned in a 2:1 ratio to receive the DEX PS DDS implant using either the updated applicator (test) or the currently-approved applicator (comparator), respectively.

2.4 Sample Size Determination

The sample size is determined empirically based on discussions with FDA to evaluate a minimum of 30 eyes using the updated applicator and a minimum of 15 eyes using the

currently approved applicator. Assuming a dropout rate of about 15% and the need to achieve 30 and 15 subjects to use the updated applicator and currently-approved applicator, respectively, the total enrollment would require approximately 54 subjects.

3.0 Endpoints

3.1 Efficacy Endpoint(s)

The study is not designed to assess efficacy of the study drug. The DEX PS DDS Implant is an FDA-approved drug, and its efficacy is already well-established.

3.2 Safety Endpoint(s)

This study is not designed to assess safety of the study drug, but AEs will be collected. The DEX PS DDS Implant is an FDA-approved drug, and its safety is already well established.

Safety variables that will be evaluated in the study include vital signs, AEs, and ocular parameters as determined through assessments of BCVA, biomicroscopic slit-lamp examination, ophthalmoscopy, and IOP.

4.0 Analysis Populations

The following population sets will be used for the analyses.

The Safety Analysis Set (SAS) consists of all subjects who received DEX PS DDS Implant. Subjects will be included in the analysis according to the updated applicator or currently-approved applicator that was used to deliver the DEX PS DDS Implant.

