3.4 Additional Endpoints

Additional endpoints are the updated and currently-approved DEX PS DDS Applicator performance (assessed via treatment administration assessment form, completed by the investigator) on Day 1. Further details regarding the treatment administration assessment form are in the Operations Manual ([Appendix F](#)).

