4.2 Discussion of Study Design

Choice of Control Group

This is a two-arm, open-label study where approximately 54 subjects will be randomized in a 2:1 ratio to receive the same DEX PS DDS implant using either an updated applicator (test arm) or the currently-approved applicator (comparator arm), respectively.

Appropriateness of Measurements

Standard statistical and clinical procedures will be utilized in this study. All measurements in this study are standard for assessing disease activity in subjects with macular edema due to RVO (BRVO or CRVO) or DME. All clinical and laboratory procedures in this study are standard and generally accepted.

Suitability of Subject Population

Adult subjects with macular edema due to RVO (BRVO or CRVO) or DME will be included in this study, consistent with the currently marked product. The SE will be selected by the investigator. Qualified subjects will be administered DEX PS DDS Implant using either the updated or currently-approved DEX PS DDS Applicator in the SE. To avoid confounding results, ocular conditions in the SE in which DEX PS DDS Implant is contraindicated are prohibited during the study.

Selection of Doses in the Study

The study will consist of a single fixed-dose administration of the DEX PS DDS Implant (0.7 mg) in the SE, which is same as the currently marketed product.

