7.2 Definition for Analysis Populations

All subjects who have received DEX PS DDS Implant will contribute to the Safety Analysis Set (SAF). The SAF will be used for all safety analyses.

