7.5 Statistical Analyses for Safety

The safety analysis will be performed using the SAF. General safety parameters will include AEs (including pregnancies that meet SAE criteria per Section 6.1) and vital signs. Ocular safety parameters will include BCVA, IOP measurement, biomicroscopy, ophthalmoscopy. The treatment administration assessment form will be collected to evaluate investigator experience with and performance of the updated and the currently-approved DEX PS DDS Applicators.

Adverse events will be coded using the Medical Dictionary for Regulatory Activities (MedDRA). The number and percentage of subjects reporting AEs will be tabulated based on primary system organ class and preferred terms. Summary tables will be generated for all AEs regardless of causality as well as treatment-related AEs. Descriptive statistics for vital signs will be presented. Ocular safety parameters will be summarized. The treatment administration assessment form will also be summarized.

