10.0 Safety Analyses

10.1 General Considerations

Safety data will be summarized for the SAS. Safety summaries will be presented by treatment group. For the safety analysis, subjects are assigned to a treatment group based on the treatment actually received, regardless of the treatment randomized.

Study eye is defined as the eye that received DEX PS DDS Implant.

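### The only analysis set requires that the implant was received, so on a literal reading a complete non-delivery cannot lower the delivery result or enter the by-applicator safety tables

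*SAP*

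**What the plan says.** Protocol 3.1 and SAP 2.1 give one objective: to demonstrate that the updated applicator delivers the implant to the vitreous cavity and is suitable for commercial use. Neither document defines a hypothesis or an estimand.

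There is one analysis set. SAP 4.0: "The Safety Analysis Set (SAS) consists of all subjects who received DEX PS DDS Implant". Subjects are grouped "according to the updated applicator or currently-approved applicator that was used to deliver the DEX PS DDS Implant". Protocol 7.2 sets the same condition under the abbreviation SAF and uses that set for all safety analyses. SAP 10.1 runs the safety summaries on it, by treatment actually received, and adds: "Study eye is defined as the eye that received DEX PS DDS Implant". SAP 10.2.1 counts events as treatment-emergent from the first dose.

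Performance is recorded on the treatment administration assessment form. Operations Manual 3.13 has the investigator state, on Day 1 after administration, whether the applicator dispensed the implant in the vitreous cavity and worked as intended. Protocol 3.4 gives the form's status: "Additional endpoints are the updated and currently-approved DEX PS DDS Applicator performance". Protocol 7.5, which opens by naming the SAF as the set for the safety analysis, says: "The treatment administration assessment form will also be summarized". The SAP contains no analysis of the form and marks Other Analyses (11.0) as not applicable.

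The sample size text counts differently. SAP 2.4 aims "to evaluate a minimum of 30 eyes using the updated applicator", with 15 for the approved applicator.

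**The concern.** Entry to the set depends on the outcome that the study exists to examine. If an applicator fails to release the implant, or the implant is lost before it enters the eye, the subject has not received it in the ordinary sense of the word. No applicator was used to deliver it either. Such a failure leaves the numerator and the denominator together, so the delivery result cannot fall however many of these failures occur.

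The event is foreseeable. The form allows the answer that the implant was not dispensed. Operations Manual 3.12 (step 7) warns that rough handling can dislodge the implant. Protocol 2.1 lists the implant retention feature among the changes, so release or loss of the implant is a plausible way for the two applicators to differ (an inference, not a statement in the documents).

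Safety has a parallel gap. If the needle enters the eye and nothing is released, adverse events are still collected (Protocol 6.1, Operations Manual 4.1). On the literal reading, though, the subject is outside the safety set and has no dose date from which to count treatment emergence. By SAP 10.1 the subject also has no study eye, although Protocol 4.2 says: "The SE will be selected by the investigator".

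**Working it through.** **1. The plan's own figure.** Inputs from Protocol 7.8 and SAP 2.4: 30 and 15 eyes, about 15% dropout, 2:1 allocation.

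- Test: 30 / 0.85 = 35.3, rounded up to 36.
- Comparator: 15 / 0.85 = 17.6, rounded up to 18.
- Total: 36 + 18 = 54.

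The stated total reproduces and is not in dispute. The planned arms of 36 and 18 serve as the numbers of attempts below.

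**2. Possible cases, with the definitions read literally.**

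| Case | In the only analysis set? | Shown in SAP 5.0 as |
|---|---|---|
| Implant released into the eye, whatever its position | Yes | Randomised, dosed |
| Needle entered the eye, implant not released | No | Randomised, not dosed |
| Implant lost or applicator damaged before eye contact | No | Randomised, not dosed |
| Randomised, administration never attempted | No | Randomised, not dosed |

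Misplaced implants stay in the set. The second and third rows are delivery failures, and SAP 5.0 has no row that separates them from the fourth.

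**3. Size, for assumed failure counts.** The documents give no failure rate and plan no confidence interval, so the counts *k* are assumptions and the intervals are illustrative. With *n* attempts, *k* complete non-deliveries and every other attempt successful:

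- literal set: (n − k)/(n − k) = 100% for any k below n;
- all attempts: (n − k)/n;
- difference: k/n.

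Exact (Clopper-Pearson) 95% intervals are in brackets. For x = n the lower limit is 0.025^(1/n); for example 0.025^(1/35) = 0.900.

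| Arm | k | Literal set | All attempts | Difference |
|---|---|---|---|---|
| Test, n = 36 | 1 | 35/35 = 100% (90.0–100) | 35/36 = 97.2% (85.5–99.9) | 2.8 points |
| Test, n = 36 | 2 | 34/34 = 100% (89.7–100) | 34/36 = 94.4% (81.3–99.3) | 5.6 points |
| Test, n = 36 | 3 | 33/33 = 100% (89.4–100) | 33/36 = 91.7% (77.5–98.2) | 8.3 points |
| Comparator, n = 18 | 1 | 17/17 = 100% (80.5–100) | 17/18 = 94.4% (72.7–99.9) | 5.6 points |

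**4. Chance that the question arises.** The probability of at least one non-delivery in 36 attempts is 1 − (1 − p)^36. For assumed true rates p of 1%, 2%, 5% and 10% it is 30%, 52%, 84% and 98%.

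**The case against.** The best defence is that *received* means *administration attempted*. The form is completed after administration and asks whether the implant was dispensed. If administration already meant delivery, an answer of no for non-release could hardly arise. Operations Manual 3.12 also has the site record the date and time of administration, which would give the treatment-emergent rule its date. On that reading nothing is lost. This stands as a fair reading, but neither document states it, and the SAP 4.0 grouping by the applicator that delivered the implant points the other way. The trial is open-label, so a rule left open would be settled with arm and outcome known.

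A second defence is that the SAF is not named as the form's denominator. That is correct. Performance is an additional endpoint, only its place in Protocol 7.5 links it to the SAF, and no delivery rate is planned. A reader might infer that the plan commits itself to a biased rate. The documents do not support that; they leave this set as the only one available.

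A reader might also infer that failures would disappear from the report. They would not. SAP 5.0 shows randomised and dosed counts and reasons for discontinuation for each treatment group, a complaint form is due within 24 hours (Operations Manual 4.2), and complaints linked to adverse events reach the study summary (Protocol 6.1). This is real visibility, but none of it is a performance rate.

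Finally, one could set the minimum of 30 eyes *using* the applicator against the count of eyes that *received* the implant and call it a contradiction. SAP 2.4 is an enrolment target and 4.0 is a set definition. The planned arms leave 36 − 30 = 6 and 18 − 15 = 3 subjects in hand, and the form is completed on Day 1, before later dropout matters. The two counts would give different answers only after that margin had gone.

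**Conclusion.** The point holds in conditional form and should be fixed. Read literally, the only analysis set is conditioned on the outcome named in the primary objective. The performance consequence needs two assumptions: that *received* excludes a failed attempt, and that the form is summarised on this set. The safety-table consequence needs only the first. It concerns the tabulation of events after needle entry without release, not their collection.

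Under those assumptions, 1 to 3 non-deliveries in the planned test arm would change the displayed result by 2.8 to 8.3 percentage points, always in the applicator's favour. The failure counts are hypothetical, and with none the two sets agree. The study is descriptive, so no test or error rate is affected. The description is, however, the evidence for the objective, and its denominator should be fixed in advance.

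**What to change.** 1. **SAP 4.0, performance set.** Add an applicator-performance set of all subjects in whom administration with a study applicator was attempted, grouped by the applicator used in the attempt. State where an attempt begins. Name this set as the denominator for the assessment form and count non-delivery as a failure, with failures before eye contact on a separate line. If more than one kit was opened for a subject, count the first attempt in the rate and list the later kit. This is a counting rule only; the documents do not address the use of a second kit.
2. **SAP 4.0, 10.1 and 10.2.1, safety set.** Include all subjects whose eye was entered by the applicator needle, whether or not the implant was released. Count treatment emergence from that procedure and define the study eye as the eye selected for treatment. Report subjects whose applicator failed before eye contact in the performance set only. Pouch opening (step 7 of the procedure) precedes needle entry (step 18), so a safety set that began at pouch opening would admit unexposed eyes.
3. **Protocol.** State in Operations Manual 3.13 that the existing form is completed after every attempt, and align Protocol 7.2 at the next amendment.

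Most of this is SAP wording, since Protocol 7.1 leaves analysis details to the SAP. The protocol and Operations Manual wording needs IRB review (Protocol 8.1). No new assessment is required, because the form and the adverse event and complaint records already exist. The cost is a little more analysis work and a performance result that may look less favourable.
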